Transfers for weighing: During the process of measuring the participant's height and weight, we will have them transfer to a mat table independently or with assistance. During the transfers, we will have a spotter for all transfers and will provide someone who has been trained to assist with transfers help if needed.

Using apps and adobe connect: During the study we will have the participants using the LoseIt! app, the E-scale app and adobe connect. LoseIt! and E-scale apps will be installed on their android device or one will be provided to them to use during the study. Non-personal logins for these devices will be provided to them so that no identifiable information is ever communicated with these apps. Adobe connect will be used to conduct weekly chat sessions with no audio or video being used. We will email the participants a link to join the chat room and ask them to join using their first names only.

5.2

What steps will be taken in the event that a clinically significant, unexpected disease or condition is identified during the conduct of the study?

* Not Applicable

5.3

All the risk questions (screening, intervention/interaction, follow-up) have been merged into one question (5.1).

[\[reviewer notes→\]](#)

5.4

Do any of the research procedures pose a physical or clinically significant psychological risk to women who are or may be pregnant or to a fetus?

* No

[\[reviewer notes→\]](#)

5.5

Do any of the research procedures pose a potential risk of causing genetic mutations that could lead to birth defects?

* No

[\[reviewer notes→\]](#)

5.6

Are there any alternative procedures or courses of treatment which may be of

benefit to the subject if they choose not to participate in this study?

* No

If **Yes**, describe in detail:

[\[reviewer notes→\]](#)

5.7

Describe the specific endpoints (e.g., adverse reactions/events, failure to demonstrate effectiveness, disease progression) or other circumstances (e.g., subject's failure to follow study procedures) that will result in discontinuing a subject's participation?

* Describe below:

If the subject is admitted to the hospital for more than 5 days we will remove them from the study. Also if the subject has not participated in any study procedures for 2 weeks they will be removed from the study.

[\[reviewer notes→\]](#)

5.8

Will any individuals other than the investigators/research staff involved in the conduct of this research study and authorized representatives of the University Research Conduct and Compliance Office (RCCO) be permitted access to research data/documents (including medical record information) associated with the conduct of this research study?

* Yes

5.8.1

Identify the 'external' persons or entity who may have access to research data/documents and the purpose of this access:

The sponsoring agency (The Paralyzed Veterans of America) may access the research data and documents.

5.8.2

Will these 'external' persons or entity have access to identifiable research data/documents?

*

No; the research data/documents will be coded and subject identifiers removed prior to access by the external persons

If **Yes**, describe how they will protect the confidentiality of the research data:

5.9

Has or will a Federal Certificate of Confidentiality be obtained for this research study?

* No

5.10

Question has been moved to 5.17

5.11

Question has been moved to 5.16

[\[reviewer notes→\]](#)

5.12

Does participation in this research study offer the potential for direct benefit to the research subjects?

Yes - Describe the direct benefit that subjects may receive as a result of study participation. Indicate if all, or only certain, of the subjects may derive this potential benefit.

Describe the benefit:

All subjects may lose weight, which could benefit their overall health

5.13

Describe the data and safety monitoring plan associated with this study. If the research study involves multiple sites, the plan must address both a local and central review process.

A data safety and monitoring plan will be implemented to ensure that there are no changes in the benefit/risk ratio during the study and that confidentiality of research data is maintained. All investigators, study personnel, and the clinical coordinators involved in the study will meet quarterly to discuss the study (e.g., study goals, progress, modifications, documentation, recruitment, retention, data analysis, and confidentiality) and address any issues or concerns at this time. The PI holds weekly lab meeting, in which progress is reviewed and issues addressed. Any instances of adverse effects will be reported immediately using the standard forms and/or procedures set forth by the Institutional Review Board. In addition, clinical coordinators will periodically review study documentation and/or consent forms to ensure that subject's confidentiality is maintained. A summary report of all data and safety monitoring activities will be included in the annual IRB renewal application.

[\[reviewer notes→\]](#)

Section 5 - Potential Risks and Benefits of Study Participation

5.14

What precautions will be used to ensure subject privacy is respected? (e.g. the research intervention will be conducted in a private room; the collection of sensitive information about subjects is limited to the amount necessary to achieve the aims of the research, so that no unneeded sensitive information is being collected, drapes or other barriers will be used for subjects who are required to disrobe)

During consent and collection of questionnaires and measurements, the subjects will be provided a private space. The collection of sensitive information about subjects is limited to the amount necessary to achieve the aims of the research, so that no unneeded sensitive information is being collected.

5.15

What precautions will be used to maintain the confidentiality of the research data during collection, transmission and storage? It is important that you indicate the data security measures for all data types.

Go to the [A-Z Guidance](#), download the Data Security Assessment Form, complete, and upload using the Add button below. Depending on the data type, you may need to consult with your data manager to address some of the sections. Email [contact] if you have any questions.

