This research will tell whether wheelchair users find the E-scale to be useful and feasible as a way to monitor their weight in their homes. It will also show whether wheelchair users, like the general population, have better weight loss outcomes if they monitor their weight daily. This could lead to refinement of the E-scale and a push for more available technology for wheelchair users to monitor their weight at home which could in turn lead to a decrease in the prevalence of obesity among wheelchair users.

[\[reviewer notes ↴\]](#)

2.1 Does this research study involve the use or evaluation of a drug, biological, or nutritional (e.g., herbal or dietary) supplement?

* No

[\[reviewer notes ↴\]](#)

2.2 Will this research use or evaluate the safety and/or effectiveness of one or more devices?

* Yes

2.2.1 Does this research study involve an evaluation of the safety and/or effectiveness of one or more devices not currently approved by the FDA for general marketing?

* Yes

If YES, describe your **plan to prevent unauthorized use of the investigational device**: The E-scale is a non-invasive device which measures the weight of each of the four legs of a bed. As such there would be no benefit or harm from unauthorized use.

2.2.1.1 List each of the unapproved devices being evaluated in this research study.

Specify for each listed device the corresponding Investigational Device Exemption (IDE) number or provide a justification for why you feel that this device and its use, as proposed in this research study constitute a non-significant risk (i.e., to include potential failure of the device) to the research subjects:

Unapproved IDE device	#	Non-significant risk justification
View E-scale		The E-scale is a set of weight sensors for each leg of a bed. This device does not have potential for serious risk to the health, safety, or welfare of a subject since (1) The device is not an implant; (2) The device is not used in supporting or sustaining human life; or (3) The device is not of substantial importance in diagnosing, curing, mitigating, or treating disease, or otherwise preventing impairment of human health. It has also been used in the home without any adverse events in IRB # PRO14080007

[\[reviewer notes ↴\]](#)

2.2.2 Does this research study involve the use or evaluation of the safety and/or effectiveness of one or more devices approved by the FDA for general marketing?

* No

[\[reviewer notes ↴\]](#)

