All members of the research team will be involved with discussing and obtaining informed consent at the beginning of the subject's initial visit. The information about the study will be described during the screening and again when the potential subject comes into the lab, and all questions answered. This will give the subjects adequate time to decide to participate or not. The subjects will provide their own consent.

4.13 Are you requesting an exception to either IRB policy related to the informed consent process?

- For studies involving a drug, device or surgical procedures, a licensed physician who is a listed investigator is required to obtain the written informed consent unless an exception to this policy has been approved by the IRB
- For all other studies, a listed investigator is required to obtain consent (Note: In order to request an exception to this policy, the study must be minimal risk)

* No

If Yes, provide a justification and describe the qualifications of the individual who will obtain consent:

4.14 Will you inform research subjects about the outcome of this research study following its completion?

* No

If Yes, describe the process to inform subjects of the results:

[\[reviewer notes\]](#)

5.1

Describe potential risks (physical, psychological, social, legal, economic or other) associated with screening procedures, research interventions/interactions, and follow-up/monitoring procedures performed specifically for this study:

*

View	
Research Activity: Consent, measurements and questionnaires
 
Common Risks: No Value Entered
 
Infrequent Risks: breach of privacy and confidentiality
 
Other Risks: No Value Entered

View	
Research Activity: Installation and removal of escale
 
Common Risks: No Value Entered
 
Infrequent Risks: damage to bed or surrounding areas
 
Other Risks: No Value Entered

View	
Research Activity: Transfers for weighing
 
Common Risks: No Value Entered
 
Infrequent Risks: Falling during transfers
 
Other Risks: No Value Entered

View	
Research Activity: Using apps and adobe connect
 
Common Risks: No Value Entered
 
Infrequent Risks: breach of privacy and confidentiality
 
Other Risks: No Value Entered

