View	
Research Activity: Using E-scale
 
Common Risks: No Value Entered
 
Infrequent Risks: Breach of privacy with motion being detected. Height of the bed is increased by approximately 1/2 inch which could make transfers more difficult.
 
Other Risks: No Value Entered

5.1.1 **Describe the steps that will be taken to prevent or to minimize the severity of the potential risks:**

Consent, measurements and questionnaires: During all activities of consent, measurements and questionnaires we will provide the subjects will a private location to answer the questions. Subject codes will be used on all data collection forms. All identifiable information will be stored in a locked file room separate from the research data. The only linkage code will be stored on a password protected department server.

Installation and removal of E-scale: The study team will visit the participants' homes to install and remove the E-scale. It is possible that during this time, damage could be caused

to the participant's bed or surrounding areas. The investigator is liable for any damage that occur as a result of participation in the study and damage will be reimbursed accordingly. During the first visit, the investigator will assess the condition of the bed and items placed near the bedside. After such verification, it is to the discretion of the investigator if he wishes to continue with installation of E-Scale or disqualify the participant due to concerns with the bed. IRB # PRO14080007 is a past study using these scales with no adverse events.

Use of E-scale: During the use of the E-scale, the bed height will be raised by approximately 1/2 in when the sensors are under the bed legs. This may make transfers to and from bed more difficult for the wheelchair users. We will describe this risk during the consent process so they are aware and can withdraw from the study if they feel it will be an issue. The E-scale also collects the weight from the bed legs continuously and as such changes in weight distribution may make it possible to detect when the person is in or out of bed and if they are moving. We will also make the participants aware of this risk during the consent process.

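### The plan names harder bed transfers as the only physical hazard of using the E-scale, but no procedure it describes asks participants about them while the scale is installed

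*Combined protocol and SAP*

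**What the plan says.** **The hazard.** Under Using E-scale, section 5.1 gives two infrequent risks. One concerns privacy, because motion can be detected. The other is physical: "Height of the bed is increased by approximately 1/2 inch which could make transfers more difficult". Section 5.1.1 repeats it for the home: "This may make transfers to and from bed more difficult for the wheelchair users".

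**The response to it.** Section 5.1.1 relies on disclosure: "We will describe this risk during the consent process so they are aware and can withdraw from the study if they feel it will be" a problem. Also in 5.1.1, the investigator looks at the bed and its surroundings at the first visit and may decide against installation. That step is written under the risk of damage to property.

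**Falls.** Section 5.1 has the entry "Infrequent Risks: Falling during transfers", but under Transfers for weighing, which take place in the laboratory. The matching safeguard in 5.1.1, "During the transfers, we will have a spotter for all transfers", is under the same heading.

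**Adverse events.** Section 5.13 states: "Any instances of adverse effects will be reported immediately using the standard forms and/or procedures set forth by the Institutional Review Board". It also provides for weekly laboratory meetings and quarterly team meetings. It does not say how an event at home comes to the team's notice.

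**Outcomes.** Section 2.17 lists survey feedback, accuracy and repeatability of the scale, and changes in weight, girth, body fat and SRAHP score. No safety item is among them.

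**The concern.** A rule for passing on adverse effects works only on events the team knows about. Here the sponsor has identified a specific way in which the device may make daily life harder, the scale stays under the bed for about 12 weeks, and the described contacts leave it to the participant to raise any problem.

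Two things are at stake. First, a participant who is struggling with transfers, or has had a near-fall, may not come to the team's attention while the scale is still in place. Second, information that was never collected cannot be recovered at analysis. If the study ends with no events on file, nobody can tell whether none occurred or none was mentioned. Statements of that kind do get reused. Section 2.2.1.1 says of the E-scale in an earlier study, "It has also been used in the home without any adverse events", and does not say how events were sought there.

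**Working it through.** The plan states no event rate, safety sample size or other figure on this point, so there is nothing to reproduce. The check has two parts.

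**Part 1. Does any described contact ask about bed transfers, near-falls or falls at home?**

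- *Emails (2.6):* encouragement, adherence, lesson material and the chat link. No safety question is described.
- *Weekly group chat (2.6):* text only, covering the lesson and a general discussion of what went well or badly. An event might surface, but nobody is asked.
- *Device problems (2.6):* started by the participant and limited to malfunction. A scale that works correctly under a raised bed is not a malfunction.
- *Follow-up procedures (2.7):* answered No.
- *Week 13 visit (2.6):* weight, girth, body fat, SRAHP and the final questionnaire, described as covering opinions of the E-scale and of parts of the study. Its items are not in the file.
- *Instruments (2.8):* EDDS, screening tool, Final Survey, CES-D, demographics and SRAHP. The System Usability Scale is among the attachments. None is described as covering transfers or falls.
- *Removal from the study (5.7):* triggered by a hospital stay of more than 5 days or 2 weeks without participation. Neither trigger records a fall as such.
- *Withdrawal (5.16):* the participant is asked to complete the final questionnaire if willing. Recording the reason for leaving is not described.
- *Monitoring plan (5.13):* onward reporting and meetings only.

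So no described procedure asks. The one place where a question could already exist is the unreproduced final questionnaire, which is given once, at week 13 or at withdrawal.

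**Part 2. What could a count show if everyone were asked?**

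Input: up to 15 enrolled (CS2.1 and 3.11). With zero events among n people who were all asked, the exact upper limit on the share of participants affected is 1 − α^(1/n).

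- n = 15, one-sided 95%: 1 − 0.05^(1/15) = 0.181, or 18.1%.
- n = 15, upper end of the two-sided 95% interval: 1 − 0.025^(1/15) = 0.218, or 21.8%.
- n = 10 (assumed, to show the effect of fewer people asked), one-sided 95%: 1 − 0.05^(1/10) = 0.259, or 25.9%.

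The chance of seeing zero among 15 with complete asking, for assumed true risks:

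- True risk 10%: 0.90^15 = 0.206.
- True risk 20%: 0.80^15 = 0.035.

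These limits come from the sample size and are the same before and after the fix. The fix makes them applicable, because the formula needs a known number of people who were asked. Without asking, the share of events that reaches the team is unknown, and the documents give no basis for a figure.

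**The case against.** The strongest reply is that the gap cannot be fully verified. The Final Survey and the System Usability Scale are uploaded instruments whose items are not in the file, and the consent form, which may tell participants to report injuries, has been removed. A transfer item would fit a survey about the E-scale. This stands, and it limits the claim to what the documents describe. It does not close the gap, because a question asked only at week 13 comes as the scale is about to be removed and depends on recall over the whole period.

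The plan is also not silent. It discloses the risk, inspects the bed, holds a weekly chat and reviews progress at laboratory meetings. That is fair, but none of these asks the question, and consent comes before anyone has used the raised bed.

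A reader might infer more than the documents support:

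- *That the plan recognises a risk of home falls.* It speaks of more difficult transfers; the step to falls is an inference from the fall risk named for laboratory transfers.
- *That participants transfer at home unaided.* The documents do not say whether they have help.
- *That leaving safety out of 2.17 contradicts the study's purpose.* The objective in 1.1 is usefulness, feasibility and efficacy, and 2.17 asks for main outcomes only.
- *That the study intends to claim the device is safe.* No section says so.

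Finally, a count in one group of at most 15 cannot establish device safety. That is correct, and it is why the count is proposed as descriptive only.

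**Conclusion.** The point holds in a limited form. The plan identifies harder transfers to and from a raised bed as the only physical hazard of using the E-scale, and no procedure described in the documents asks about it during the weeks of use. An event could go unrecorded, and a statement of no events would be hard to interpret.

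The size is modest. The hazard is listed as infrequent, arises from about half an inch of height, and sits in an exploratory study classed as minimal risk. Even with complete asking, zero events in 15 would leave risks up to about 18% unexcluded (one-sided 95%), and background events could not be told apart from device-related ones. The gain is in validity and timely notice, not precision.

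The conclusion rests on two assumptions: that the unreproduced instruments match their descriptions, and that harder transfers can plausibly lead to near-falls or falls. If the final questionnaire does cover transfers, what remains is the lack of any question while the scale is in use. The recommendation is a cheap improvement on patient-safety grounds, not a correction of an error.

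**What to change.** In 2.6 and 5.13, add one scripted question on difficulty, near-falls or falls during bed transfers since the last contact. Put it in a private individual contact, such as the email already sent to participants. It should not go in the group chat, where participants join by first name and an answer would disclose a health event to the others. Repeat the question in the final questionnaire and at withdrawal.

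As a secondary safety item alongside 2.17 and 2.18, report the number of participants with an event out of the number asked, with an exact confidence interval. State beside it that at most 15 people without a control group cannot exclude a risk of about 18% when no events are seen (one-sided 95%), and cannot attribute events to the device.

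The cost is one question in contacts that already exist, and a few extra reports to review.

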*** Upload Data Security Form:**

Name Modified Date
Data Security Assessment form 10/10/2017 11:04 AM

Address what precautions will be used to maintain the confidentiality of the research data collected in paper format if applicable:

Records will be coded by assigning a case number unique to this study. The linkage code will be stored electronically and not with other paper based files. All electronic data will be stored on the University of Pittsburgh network. Paper based records will be kept in a locked file room within the Human Engineering Research Laboratories. Access to both the electronic and paper based files is restricted to the Principal Investigator and the associated research staff working on the project.

5.15.1

Does your research study require a data security review? Answer Yes if any of the following conditions are met:

- Identifiable or *coded data will be collected, stored, or transmitted using any of the following technologies: mobile app, web-based site or survey, wearable device, text messaging, electronic audio, photographic, or video recording or conferencing **and/or**
- The IRB requested a data security review during their review of the study

* Yes

***Coded:** Identifying information (such as name) that would enable the investigator to readily ascertain the identity of the individual to whom the private information or specimens pertain has been replaced with a code (number, letter, symbol, or any combination) and a key to decipher the code exists, enabling linkage of the identifying information to the private information or specimens

5.16

If the subject withdraws from the study, describe what, if anything, will happen to the subject's research data or biological specimens.

If the subject withdraws from the study, any existing data will be rendered anonymous and included in results. We will ask the participant to answer the final questionnaire if they are willing to. Because this is a usefulness, feasibility and efficacy trial, even partial data could provide us with useful results.

5.17

Following the required data retention period, describe the procedures utilized to protect subject confidentiality. (e.g., destruction of research records; removal of identifiers; destruction of linkage code information; secured long-term retention)

Following the data retention period, the linkage code file will be deleted. Data will be retained for a longer term using the security measures already outlined in section 5.15.

